8.4.6. Adverse Events of Special Interest

All AESIs should be reported according to the procedures and timelines for SAEs (see Section 10.3.4). Detailed narratives will be written for any participant who develops an AESI.

The following events will be reported as AESIs:

- AEs that result in the discontinuation of IMP
- Events that satisfy the criteria for suspected Hy's Law (alanine aminotransferase [ALT] or aspartate aminotransferase [AST] >3 × upper limit of normal [ULN], AND serum bilirubin ≥2 × ULN
 - Repeat for confirmation and notify the medical monitor immediately
- QTcF >500 ms or increase >60 ms from baseline
 - Repeat for confirmation and notify the medical monitor immediately
- Grade 2 moderate AEs that are related to the gastrointestinal system (eg, nausea, vomiting, diarrhea, constipation, dyspepsia, etc)
- Grade 2 moderate AEs that are related to the central nervous system (eg, headache, dizziness, syncope, irritability, anxiety, etc)
- AEs potentially related to abuse (refer to the APMP document for details)

The primary objective of the APMP is to monitor events that may suggest that CVL-354 produces drug effects that could be sought out for abuse purposes. In addition to monitoring for irregularities in medication handling, AEs that may be suggestive of a developing abuse issue

will also receive special attention. As part of the APMP, AEs potentially related to abuse and medication handling irregularities related to suspected or known abuse of IMP must be reported as AESIs. Investigators and site staff at each trial site will be trained on reporting potentially abuse-related AEs. While the investigators will be provided with examples of AE terms as a guide during trial conduct, the analysis of potentially abuse-related AEs will be based on a search by the sponsor of all relevant Medical Dictionary for Regulatory Activities (MedDRA) terms, all verbatim terms, and any open text fields within the AE data to identify text strings suggestive of abuse potential, consistent with US FDA guidance (FDA Guidance for Industry, 2017).

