10.3.2. Definition of SAE

If an event is not an AE per definition above, then it cannot be an SAE even if serious conditions are met (eg, hospitalization for signs/symptoms of the disease under trial, death due to progression of disease).

Table 15: Definition of SAE

An SAE is defined as any untoward medical occurrence that, at any dose in the view of either the investigator or sponsor, results in any of the following outcomes:

a. Results in death

b. Is life-threatening

The term "life-threatening" in the definition of "serious" refers to an event in which the participant was at risk of death at the time of the event. It does not refer to an event, which hypothetically might have caused death, if it were more severe.

c. Requires inpatient hospitalization or prolongation of existing hospitalization

In general, hospitalization signifies that the participant has been detained (usually involving at least an overnight stay) at the hospital or emergency ward for observation and/or treatment that would not have been appropriate in the physician's office or outpatient setting. Complications that occur during hospitalization are AEs. If a

complication prolongs hospitalization or fulfills any other serious criteria, the event is serious. When in doubt as to whether "hospitalization" occurred or was necessary, the AE should be considered serious.

Hospitalization for elective treatment of a pre-existing condition that did not worsen from baseline is not considered an AE.

d. Results in persistent disability/incapacity

The term disability means a substantial disruption of a person's ability to conduct normal life functions.

This definition is not intended to include experiences of relatively minor medical significance such as uncomplicated headache, nausea, vomiting, diarrhea, influenza, and accidental trauma (eg, sprained ankle) which may interfere with or prevent everyday life functions but do not constitute a substantial disruption.

e. Is a congenital anomaly/birth defect

f. Other situations:

Medical or scientific judgment should be exercised in deciding whether SAE reporting is appropriate in other situations such as important medical events that may not be immediately life-threatening or result in death or hospitalization but may jeopardize the participant or may require medical or surgical intervention to prevent one of the other outcomes listed in the above definition. These events should usually be considered serious.

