 - O Any new SAEs/AESIs reported to the investigator that occur after the last scheduled contact and are determined by the investigator to be related to the use of the IMP, should be reported to the sponsor. This may include SAEs/AESIs that are captured on follow-up telephone contact or at any other time point after the defined trial period. The investigator should follow SAEs/AESIs identified after the defined trial period and continue to report any significant follow-up information to the sponsor until the events are resolved or stabilized, or the participant is lost to follow-up or has died.
- It is not acceptable for the investigator to send photocopies of the participant's medical records to the sponsor or designee in lieu of completion of the AE/SAE/AESI eCRF page.
- There may be instances when copies of medical records for certain cases are requested by the sponsor or
 designee. In this case, all participant identifiers, with the exception of the participant number, will be
 redacted on the copies of the medical records before submission to the sponsor or designee.

Assessment of Severity

All AEs, including clinically significant treatment-emergent laboratory abnormalities, will be graded according to the National Cancer Institute-Common Terminology Criteria for Adverse Events, version 5.0 (NCI-CTCAE v5.0; https://ctep.cancer.gov/protocoldevelopment/electronic_applications/docs/CTCAE v5 Quick Reference 5x7.pdf)

Adverse events not listed by the NCI-CTCAE will be graded according to the criteria defined below.

Grade	Description
1	Mild; asymptomatic or mild symptoms; clinical or diagnostic observations only; intervention not indicated.
2	Moderate; minimal, local or noninvasive intervention indicated; limiting age-appropriate instrumental activities of daily living.
3	Severe or medically significant but not immediately life-threatening; hospitalization or prolongation of hospitalization indicated; disabling; limiting self-care activities of daily living.
4	Life-threatening consequences; urgent intervention indicated.
5	Fatal AE; an event that results in the death of the participant.

Note: An instrumental activity of daily living refers to preparing meals, shopping for groceries or clothes, using the telephone, managing money, etc.

Assessment of Causality

- The investigator is obligated to assess the relationship between trial treatment and each occurrence of each AE/SAE/AESI.

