10.3.4. Reporting of SAEs and AESIs

Table 18: SAE/AESI Reporting to the Sponsor or Designee via an Electronic Data Collection Tool

SAE/AESI Reporting to the Sponsor or Designee via an Electronic Data Collection Tool

- The primary mechanism for reporting an SAE/AESI to the sponsor or designee will be the electronic data collection tool.
- The site will enter the SAE/AESI data as soon as it becomes available within 24 hours of awareness.
- If the electronic data collection tool is unavailable, then the site will use the paper SAE/AESI form (see next section).
- After the trial is completed at a given site, the electronic data collection tool will be taken off-line to
 prevent the entry of new data or changes to existing data.
- If a site receives a report of a new SAE/AESI from a trial participant or receives updated data on a
 previously reported SAE/AESI after the electronic data collection tool has been taken off-line, then the
 site can report this information on the paper SAE/AESI form (see next section) or to the sponsor or
 designee by telephone.

Table 19: SAE/AESI Reporting to the Sponsor or Designee via Paper Form (if needed)

SAE/AESI Reporting to the Sponsor or Designee via Paper Form

- If the electronic data collection tool is unavailable, then the site will use the paper SAE/AESI form. The SAE or AESI paper form should be used to electronically transmit this information to the sponsor or designee.
- Contacts for electronic transmission of the paper SAE/AESI form are provided in the Operations Manual.
- In rare circumstances and in the absence of facsimile equipment, notification by telephone is acceptable
 with a copy of the SAE or AESI data collection tool sent by overnight mail or courier service.
- Initial notification via telephone does not replace the need for the investigator to complete and sign the appropriate SAE or AESI form within the designated reporting time frames.

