### 3.4.6. Adverse Events (AEs)

An AE is defined as any untoward medical occurrence in a patient or clinical trial subject, temporally associated with the use of trial intervention, whether considered related to the trial intervention.

All adverse events will be recorded on the ADVERSE EVENTS CRF. Adverse events with missing severity will have the severity imputed as 'Grade 3' for the AE tabulations. Adverse events with missing relationship to IMP will have the relationship imputed as 'Related' for the AE tabulations if the AE started on or after the first dose of IMP. However, in the data listings these missing intensity and/or relationship will be presented as missing.

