#### 3.4.6.1. Adverse Events of Special Interest

The following events will be reported as AESIs:

- AEs that result in the discontinuation of IMP
- Events that satisfy the criteria for suspected Hy's Law (alanine aminotransferase [ALT] or aspartate aminotransferase [AST]  $>3 \times$  upper limit of normal [ULN], AND serum bilirubin  $\geq 2 \times$  ULN
  - Repeat for confirmation and notify the medical monitor immediately
- QTcF  $>500$  ms or increase  $>60$  ms from baseline
  - Repeat for confirmation and notify the medical monitor immediately
- Grade 2 moderate AEs that are related to the gastrointestinal system (eg, nausea, vomiting, diarrhea, constipation, dyspepsia, etc)
- Grade 2 moderate AEs that are related to the central nervous system (eg, headache, dizziness, syncope, irritability, anxiety, etc)
- AEs potentially related to abuse (refer to the APMP document for details)

The primary objective of the APMP is to monitor events that may suggest that CVL-354 produces drug effects that could be sought out for abuse purposes. In addition to monitoring for irregularities in medication handling, AEs that may be suggestive of a developing abuse issue will also receive special attention. As part of the APMP, AEs potentially related to abuse and medication handling irregularities related to suspected or known abuse of IMP must be reported

as AESIs. Investigators and site staff at each trial site will be trained on reporting potentially abuse-related AEs. While the investigators will be provided with examples of AE terms as a guide during trial conduct, the analysis of potentially abuse-related AEs will be based on a search by the sponsor of all relevant Medical Dictionary for Regulatory Activities (MedDRA) terms, all verbatim terms, and any open text fields within the AE data to identify text strings suggestive of abuse potential, consistent with US FDA guidance ([FDA, 2017](#)).

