### 5.9.1. Adverse Events

Adverse events will be mapped to a Medical Dictionary for Regulatory Activities (MedDRA) version 25.1 or later by system organ class, preferred term, and severity. If a subject experiences multiple events that map to a single preferred term, the greatest Common Terminology Criteria for Adverse Events (CTCAE) toxicity grade and strongest investigator assessment of relation to IMP will be assigned to the preferred term for the appropriate summaries. Events with missing severity or relationship, will be classified as outlined in [Section 4.1.1.1](#).

For Part A, all TEAEs will be attributed to a treatment period based on start date as specified in [Section 4.2.1](#). Any TEAE occurring during the washout period will be attributed to the treatment most recently administered.

The occurrence of TEAEs will be summarized by treatment group for Part A and Part B, using preferred terms, system organ class, and severity. Separate summaries of TEAEs, treatment-emergent serious adverse events (TESAEs), TEAEs by severity, TEAEs related to IMP, AESIs, and events leading to the discontinuation of study will be generated by system organ class and preferred terms. For Part B, a separate analysis of AEs leading to the discontinuation of IMP will be provided.

All AEs reported will be listed for individual subjects showing both verbatim and preferred terms and treatment group at onset of the AE. All AEs that occurred prior to the initiation of IMP will be excluded from the tables but will be included in the listings.

Missing onset dates will be imputed as previously outlined in [Section 4.1.1.2](#) as required to determine treatment-emergent events.

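### GI and CNS AESIs are defined as Grade 2 only, so a non-serious Grade 3 event can miss the AESI table, 24-hour entry and narrative that a milder event receives

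*Protocol*

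**What the plan says.** Protocol 8.4.6 names six kinds of AESI. Two are defined by body system and grade: "Grade 2 moderate AEs that are related to the gastrointestinal system" and the equivalent CNS class. SAP 3.4.6.1 carries the same list, including "Grade 2 moderate AEs that are related to the central nervous system". The other four are events leading to IMP discontinuation, suspected Hy's Law cases, QTcF prolongation and potentially abuse-related events.

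AESI status has consequences:

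- **Reporting.** AESIs follow SAE procedures and timelines. Under Protocol 10.3.4, "The site will enter the SAE/AESI data as soon as it becomes available within 24 hours of awareness".
- **Narrative.** Protocol 8.4.6: "Detailed narratives will be written for any participant who develops an AESI".
- **Tabulation.** SAP 5.9.1 plans separate summaries, among them "TEAEs by severity, TEAEs related to IMP, AESIs, and events leading to the discontinuation of study will be generated".
- **Follow-up.** Under Protocol 10.3.3, AESIs are followed until resolved or stabilized. Other non-serious events still open at the last scheduled contact are recorded as ongoing.

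**The concern.** The class boundary has a floor and, as written, also a ceiling. Moderate GI and CNS events are in and severe ones are not mentioned, so the definition ranks severity the wrong way round. GI and CNS events were added as AESIs in protocol Version 2.0 to improve understanding of the safety profile (Protocol Appendix 8). A rule that can drop the worse cases works against that purpose. A reader who uses the AESI table to compare tolerability across doses could see a falling count when events are in fact becoming more severe. The sponsor would also lack the expedited report and narrative for the events it most needs to understand.

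**Working it through.** The plan has no figure to reproduce here. The check sets the texts side by side, followed by short design arithmetic.

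**1. Does 'Grade 2' mean a threshold?** Nothing says so.

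- The grade scale in Protocol 10.3.3 labels Grade 2 moderate and Grade 3 severe, so the AESI wording names a single grade by both number and label.
- Protocol 4.4 has separate stopping criteria for Grades 2, 3 and 4.
- Where the SAP wants a minimum grade it states one: its definition of treatment-emergent laboratory toxicity specifies Grade 1 as a minimum when baseline is missing.

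**2. Can a Grade 3 GI or CNS event be non-serious?** Yes, on the protocol's own text.

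- The Grade 3 description in Protocol 10.3.3, which applies to events not listed in CTCAE, reads in part "hospitalization or prolongation of hospitalization indicated; disabling; limiting self-care activities of daily living". Limitation of self-care is enough; hospitalization is not required.
- On the disability criterion for an SAE, Protocol 10.3.2 says "This definition is not intended to include experiences of relatively minor medical significance such as uncomplicated headache, nausea, vomiting, diarrhea".
- Severity and seriousness are assessed separately, and Grade 3 alone does not make an event an SAE.

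**3. Does another AESI item catch it?** Only if the event leads to IMP discontinuation, is potentially abuse-related, or meets the Hy's Law or QTcF item. The discontinuation item cannot apply to an event that starts after a participant's last dose: after dosing in SAD Period 4 or food-effect Period 2, or after Day 14 in Part B.

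**4. Grades 4 and 5.** These are life-threatening or fatal, so they reach the sponsor within 24 hours as SAEs. They too fall outside the GI and CNS classes as written. The practical gap is at Grade 3.

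**5. Missing severity.** SAP 3.4.6 states: "Adverse events with missing severity will have the severity imputed as 'Grade 3' for the AE tabulations". The SAP does not say whether the AESI table uses site-reported AESIs or graded AE data. If it uses graded data, this conservative imputation would move a GI or CNS event of unknown grade out of the table.

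**6. Size per omitted participant.**

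- Part B: 8 active per dose. Food effect: 8 participants, each dosed fed and fasted. Either way 1/8 = 0.125, or 12.5 points.
- SAD: Protocol Table 8 has 4 sequences of 2, and each dose is given in 3 of them, so 3 × 2 = 6 active. 1/6 = 0.167, or 16.7 points.

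**7. Illustrations (counts chosen for the example, not predicted).**

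| Scenario | As written | Grade 2 or higher |
|---|---|---|
| One Part B dose: 2 participants with Grade 2, 1 with non-serious Grade 3 | 2/8 = 25% | 3/8 = 37.5% |
| Lower dose: 3 participants with Grade 2 | 3/8 = 37.5% | 3/8 = 37.5% |
| Next dose: 3 participants with non-serious Grade 3 | 0/8 = 0% | 3/8 = 37.5% |

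In the last two rows the AESI table appears to show tolerability improving while severity rises.

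**The case against.** The strongest reply is that little depends on this. The omitted event still appears in the TEAE and by-severity tables, in the related-TEAE table if related, and in the listings. Protocol 4.4 counts drug-related Grade 3 events in 2 or more active participants whether or not they are AESIs, so the three-participant example would already meet that criterion if the events were related. The Safety Review Team reviews data after every dose, Protocol 6.6 halts dosing for consistent notable events attributed to the drug, and Protocol 8 requires immediate safety concerns to be raised with the sponsor. Protocol 8.4 also keeps the investigator responsible for following up IMP-related events. All of this stands, and it limits the loss to AESI handling. None of it supplies the AESI tabulation or narrative, and raising an immediate concern depends on judgment.

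Other points stand in part:

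- The Grade 3 description covers only events absent from CTCAE, and the documents do not reproduce CTCAE v5.0. The SAE text concerns uncomplicated events of minor significance and advises treating important medical events as serious. A non-serious Grade 3 event therefore remains possible, but its frequency is unknown.
- The 1/8 and 1/6 figures are the weight of one participant in any table. They show sensitivity, not expected loss.
- SAD escalation was complete at protocol Version 3.0, so no amendment can recover expedited reports for those doses. The AESI table for them can still be corrected.
- The imputation point applies only if the table is derived from grade.

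**Conclusion.** The concern holds. Followed literally, both documents deny a non-serious Grade 3 GI or CNS event that meets no other AESI item the 24-hour entry, narrative and AESI tabulation given to a Grade 2 event. The sponsor probably meant Grade 2 or higher, but no text says so. Each such participant lowers AESI incidence by 12.5 points in a Part B or food-effect group and 16.7 points at a SAD dose, assuming the planned group sizes are achieved. No event rate is assumed, and expected frequency cannot be derived from the documents. No primary analysis or escalation criterion changes. This is a stated rule that can give the wrong result, not a missing detail, and it should be fixed.

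**What to change.** - **Protocol 8.4.6 and SAP 3.4.6.1:** write 'Grade 2 or higher' for both the GI and the CNS class. This is the essential change.
- **SAP 5.9.1:** state the source of the AESI table. Preferably derive its GI and CNS part from the AE data with a prespecified term list covering the protocol's examples. Count any participant with at least one event of Grade 2 or higher, including one whose severity was imputed as Grade 3. SAP 3.4.6.1 already plans a sponsor-side search for abuse-related events, so this is the same kind of step. The definition change is worth making even without it.

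The cost is a small wording change per class in each document, an SAP derivation rule with its term list, and a few more 24-hour entries and narratives. If the protocol cannot be amended in time, the SAP change alone corrects only the table, and only if the table is derived from graded data. It would not recover expedited reports or narratives. The departure from the protocol definition should then be stated in the SAP and the study report, because the table may differ from the site-reported AESIs.

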8.5. Treatment of Overdose

An overdose is defined as a known deliberate or accidental administration of investigational drug, to or by a trial participant, at a dose above that which is assigned to that individual participant according to the protocol.

There is no specific antidote for overdose with CVL-354. In the event of an overdose, treatment should consist of general supportive measures. The investigator should complete the following:

- 1. Contact the medical monitor immediately
- 2. Closely monitor the participant for any AE/SAE and clinically significant vital signs, ECG, or laboratory abnormalities. Additional safety procedures may need to be performed at the investigator's discretion.
- 3. Document the quantity of the excess dose as well as the duration of the overdose (if multiple time points) in the eCRF

Decisions regarding dose interruptions or modifications will be made by the investigator in consultation with the medical monitor based on the clinical evaluation of the participant.

8.6. Pharmacokinetics

This section includes descriptions of the blood and urine samples obtained for PK assessments, including metabolite scouting.

All PK samples should be obtained at the exact nominal time relative to dosing. Samples obtained within 10% of the nominal time point (eg, within 6 minutes of a 60-minute sample) will not be considered a protocol deviation, as long as the exact time of sampling is captured in the source documents.

Plasma and urine samples will be processed, stored, and shipped to the bioanalytical facility according to the instructions provided to the investigator in advance of the trial. A fully validated bioanalytical method will be used to quantitate the concentrations of CVL-354 in plasma and in urine. Plasma and urine PK samples from this trial may be used for further evaluation of bioanalytical methods and identification of additional metabolites. Plasma samples from this trial may be stored up to 1 year after completion of the clinical study report (CSR).

The results from metabolite scouting work (plasma and urine) will be captured in an exploratory metabolite scouting report, which will not be included in the CSR.

Plasma concentration data from this trial combined with other data may also be used to build and/or update a population PK model for CVL-354 for the purpose of further characterizing the PK or PK/pharmacodynamic behavior of the compound. Any population PK assessment will be described in a separate report.

Statistical analyses of PK parameters are briefly described in Section 9.4.3.

